5.4 Duration of Therapy

In the absence of treatment delays due to adverse event(s), subjects may continue on the study as long as they are tolerating the drugs and responding to treatment, or until one of the following criteria are met:

- Disease progression,
- Intercurrent illness that prevents further administration,
- More than 2 dose reductions required for toxicity (as described in Section 5.1) or unacceptable toxicity
- Patient decides to withdraw from the study, or
- General or specific changes in the patient's condition render the patient unacceptable for further treatment in the opinion of the principal investigator.

5.5 Duration of Follow-up

Patients will be followed for 30 days after the last dose is administered or until one of the following occurs: patient enrolls on another protocol, patient receives standard of care, or death, whichever comes first. The follow-up will consist of a phone call between Days 27-30 after the last dose to evaluate adverse events that were ongoing and any new events that might be deemed related to the therapy. Unacceptable toxicities (i.e., AEs related to the intervention) that have not resolved by Day 30 post-treatment will be followed via biweekly phone calls until stabilization or resolution.

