7.2.2.1 Expedited Reporting Guidelines

Use the NCI protocol number and the protocol-specific patient ID assigned during trial registration on all reports.

Note: A death on study requires both routine and expedited reporting, regardless of causality. Attribution to treatment or other cause must be provided.

Death due to progressive disease should be reported as **Grade 5 “Disease progression”** in the system organ class (SOC) “General disorders and administration site conditions.” Evidence that the death was a manifestation of underlying disease (e.g., radiological changes suggesting tumor growth or progression; clinical deterioration associated with a disease process) should be submitted.

Phase 1 and Early Phase 2 Studies: Expedited Reporting Requirements for Adverse Events that Occur on Studies under an IND/IDE within 30 Days of the Last Administration of the Investigational Agent/Intervention ^{1, 2}

FDA REPORTING REQUIREMENTS FOR SERIOUS ADVERSE EVENTS (21 CFR Part 312)

NOTE: Investigators **MUST** immediately report to the sponsor (NCI) **ANY** Serious Adverse Events, whether or not they are considered related to the investigational agent(s)/intervention (21 CFR 312.64)

An adverse event is considered serious if it results in **ANY** of the following outcomes:

- 1) Death
- 2) A life-threatening adverse event
- 3) An adverse event that results in inpatient hospitalization or prolongation of existing hospitalization for ≥ 24 hours
- 4) A persistent or significant incapacity or substantial disruption of the ability to conduct normal life functions
- 5) A congenital anomaly/birth defect.
- 6) Important Medical Events (IME) that may not result in death, be life threatening, or require

hospitalization may be considered serious when, based upon medical judgment, they may jeopardize the patient or subject and may require medical or surgical intervention to prevent one of the outcomes listed in this definition. (FDA, 21 CFR 312.32; ICH E2A and ICH E6).

ALL SERIOUS adverse events that meet the above criteria MUST be immediately reported to the NCI via electronic submission within the timeframes detailed in the table below.

Hospitalization	Grade 1 and Grade 2 Timeframes	Grade 3-5 Timeframes
Resulting in Hospitalization \geq 24 hrs	10 Calendar Days	24-Hour 5 Calendar Days
Not resulting in Hospitalization \geq 24 hrs	Not required	

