NOTE: Protocol specific exceptions to expedited reporting of serious adverse events are found in the Specific Protocol Exceptions to Expedited Reporting (SPEER) portion of the CAEPR.

Expedited AE reporting timelines are defined as:

- “24-Hour; 5 Calendar Days” - The AE must initially be submitted electronically within 24 hours of learning of the AE, followed by a complete expedited report within 5 calendar days of the initial 24-hour report.
- “10 Calendar Days” - A complete expedited report on the AE must be submitted electronically within 10 calendar days of learning of the AE.

¹Serious adverse events that occur more than 30 days after the last administration of investigational agent/intervention and have an attribution of possible, probable, or definite require reporting as follows:

Expedited 24-hour notification followed by complete report within 5 calendar days for:

- All Grade 3, 4, and Grade 5 AEs

Expedited 10 calendar day reports for:

- Grade 2 AEs resulting in hospitalization or prolongation of hospitalization

²For studies using PET or SPECT IND agents, the AE reporting period is limited to 10 radioactive half-lives, rounded UP to the nearest whole day, after the agent/intervention was last administered.

Footnote “1” above applies after this reporting period.

Effective Date: May 5, 2011

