12.1 Data Reporting

12.1.1 Method

This study will be monitored by the Clinical Data Update System (CDUS) version 3.0. Cumulative CDUS data will be submitted quarterly to CTEP by electronic means. Reports are due January 31, April 30, July 31, and October 31. Instructions for submitting data using the CDUS can be found on the CTEP Web site (<http://ctep.cancer.gov>).

Note: All adverse events that have occurred on the study, including those reported through CTEP-AERS, must be reported via the monitoring method identified above.

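### The post-treatment safety call in Section 5.5 asks for less than Sections 7.2.2.1 and 12.1.1 require to be reported for the same 30 days

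*Combined protocol and SAP*

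**What the plan says.** **The planned contact.** Section 5.5 states: "The follow-up will consist of a phone call between Days 27-30 after the last dose". Its purpose is "to evaluate adverse events that were ongoing and any new events that might be deemed related to the therapy". Follow-up runs for 30 days unless it ends sooner because "patient enrolls on another protocol, patient receives standard of care, or death, whichever comes first". After Day 30, only unresolved toxicities related to the intervention are followed, by calls every two weeks.

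**The reporting duty.** The expedited-reporting table in Section 7.2.2.1 is headed as covering "Adverse Events that Occur on Studies under an IND/IDE within 30 Days of the Last Administration of the Investigational Agent/Intervention". Within it, investigators must report any serious event to the sponsor "whether or not they are considered related to the investigational agent(s)/intervention (21 CFR 312.64". Deaths are treated the same way: "A death on study requires both routine and expedited reporting, regardless of causality". Footnote 1 to that table sets an attribution condition, but only for serious events that "occur more than 30 days after the last administration of investigational agent/intervention and have an attribution of possible, probable, or definite".

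**Routine reporting.** Section 12.1.1 has no attribution condition: "All adverse events that have occurred on the study, including those reported through CTEP-AERS, must be reported via the monitoring method identified above".

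**The calendar.** Section 10 marks an adverse event evaluation in its Off Study column, with no limit by relatedness. It does not say when that evaluation takes place, and it does not tie it to the call.

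**The concern.** The call is the one contact that Section 5.5 plans for every patient after the last dose, and so the main planned means by which the site learns of events in that period. If its prompt covers new events only when they might be related, staff who follow the text as written have no instruction to ask about the rest. The relatedness judgement then comes before the event is recorded. Section 7.2.1 works in the other order: it gives five attribution categories, including unlikely and unrelated, to be assigned to events already in hand.

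In an open single-arm study the treating team makes that judgement knowing the treatment. An event that is never elicited cannot be reviewed or re-attributed later. At stake is the completeness of post-treatment safety data, including serious events that Section 7.2.2.1 makes reportable whatever their cause.

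**Working it through.** The plan gives no figure on this point, so the check is mainly a comparison of text, with one small piece of arithmetic.

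**1. Is it the same window?** Section 5.5 follows patients for 30 days after the last dose. Section 7.2.2.1 covers events within 30 days of the last administration. The windows coincide, except that Section 5.5 lets follow-up stop early when the patient joins another protocol or receives standard of care. Section 7.2.2.1 states no such early end.

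**2. Which new events are in scope?**

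| Source | Period after last dose | New events in scope | Limited by attribution? |
|---|---|---|---|
| 5.5, the call | up to Day 30 | those that might be related | Yes |
| 7.2.2.1, main rule | up to Day 30 | any serious event; any death on study | No |
| 7.2.2.1, footnote 1 | after Day 30 | serious events of at least possible attribution, by grade | Yes |
| 12.1.1 | while on study | all adverse events | No |
| 10, Off Study column | not stated | adverse events generally | No |

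Section 5.6 lists completion of the 30-day follow-up as a reason for removal from study. A patient who completes follow-up is therefore still on study during those 30 days, and Section 12.1.1 applies to them.

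**3. Do the stated exceptions explain the difference?** No. The SPEER list and Section 7.2.2.2 exempt events from expedited reporting by term and grade. The timeframe table also drops Grade 1 and 2 events without hospitalization of at least 24 hours. None of these depends on attribution.

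**4. How much of the window can fall after the call?** For a call on Day d, the days left are 30 − d:

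- Day 27: 30 − 27 = 3 days, 3/30 = 10%
- Day 28: 30 − 28 = 2 days, 2/30 = 6.7%
- Day 29: 30 − 29 = 1 day, 1/30 = 3.3%
- Day 30: 30 − 30 = 0 days

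The 10% is a share of days, not of events, and it is the worst case that Section 5.5 permits.

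**5. Can a loss of events be estimated?** No. The documents give neither the number of new post-treatment events nor the share judged unrelated. If that share were u and the call were the only source, the recorded share would be 1 − u, which only restates whatever is assumed for u. The call is also not the only possible source.

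**The case against.** The strongest reply is that Section 5.5 describes the purpose of a call and overrides nothing. Sections 7.2.2.1 and 12.1.1 bind independently, the expedited clock runs from learning of the event, and Section 7.3.3 separately requires deaths within 30 days to be reported unless they are due to progressive disease. Nothing in Section 5.5 permits a site to discard an unrelated event it hears of, so a site can comply with all of these sections. This stands. It limits the point to what the call is set up to find.

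The calendar is the second reply. Its Off Study adverse event evaluation is unfiltered, and for a patient who completes the 30 days it could well fall at the end of the window. That may be the intention, but it is not stated. The same column lists a physical exam and laboratory tests, which do not fit a phone call. The calendar softens the point without settling it.

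Third, the wording is fairly inclusive. It covers events that might be related, and on the Section 7.2.1 scale even the possible category means that the event may be related. What falls outside is events thought unlikely to be related or unrelated. That is still a screen by attribution, and for serious events Section 7.2.2.1 does not allow one before Day 30.

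Fourth, the reach is small. Section 2.4 says that accrual is closed and that two pediatric patients and one adult were still on drug. Section 13 plans no toxicity estimate or safety stopping rule that would use these counts. Both facts are correct and bear on priority.

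A reader might go further and infer that unrelated events never reached the reporting system, or that a known fraction of post-treatment events was lost. The documents support neither. They show a mismatch in instructions, not what sites did.

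**Conclusion.** The inconsistency is real. For the 30 days after the last dose, the contact planned in Section 5.5 has a narrower scope for new events than Section 7.2.2.1 sets for serious events and Section 12.1.1 sets for all events. The protocol's own attribution limit, in footnote 1, begins only after Day 30. Up to 3 days of the window can also follow the call.

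The size is modest. The consequence is confined to the completeness of post-treatment safety data, and the response-rate analysis does not depend on it. The conclusion assumes that Section 5.5 is applied as written and that the Off Study evaluation does not already serve as an unfiltered Day 30 review. If the sponsor can show that it did, what remains is a correction of wording. The change is still worth making, because it costs little and removes a conflict with a mandatory reporting rule.

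**What to change.** - **Section 5.5, scope.** State that the call records all new adverse events since the last dose as well as ongoing ones, and that relatedness is assigned afterwards on the Section 7.2.1 scale. Keep the relatedness limit only for follow-up after Day 30, as footnote 1 does.
- **Section 5.5, timing.** Time the contact so that it covers the full 30 days.
- **Sections 5.6 and 10.** Align removal from study with the new timing, so that a patient is not taken off study before the contact is made. Say how events up to Day 30 are obtained when follow-up ends early. State when the Off Study evaluation takes place and whether it is the same contact as the call.
- **Reporting.** Describe post-treatment event counts already collected as possibly incomplete for events judged unrelated.

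**Cost.** The number of calls need not change, and a few more unrelated events will be recorded. The edit touches three places rather than one sentence, because the timing cannot be moved without Section 5.6 and the calendar. Prospectively it applies to the three patients that Section 2.4 reports as still on drug.

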5.6 Criteria for Removal From Study

Patients will be removed from study for one of the following reasons: completed 30-day follow-up period, toxicities are unresolved but stabilized, patient enrolls on another protocol, or patient receives standard of care. The reason for study removal and the date the patient was removed must be documented in the Case Report Form and communicated to Central Registration per Section 3.5.

6 Human Subjects Protection

6.1 Rationale for Subject Selection

This study will be open to all individuals regardless of gender, ethnicity, or race provided that the aforementioned inclusion and exclusion criteria are met. For safety reasons, pregnant women are excluded from this study. This study will be recruited through internal referral, our physician referral base, and through various cancer information hotlines (i.e., Clinical Studies Support Center, [name].) Participants should realize that there is no guarantee of benefit to them from participation in this trial. The results of this trial may benefit future cancer patients. To date, there is no information that suggests that differences in drug metabolism or effect on tumor would be expected in one ethnic group compared to another. Efforts will be made to extend accrual to each representative population, but a balance must be struck between participant safety considerations and limitations on the number of individuals exposed to potentially ineffective treatments on the one hand and the need to explore racial/ethnic aspects of clinical research on the other hand. If differences in outcome that correlate to ethnic identity are noted, a follow-up study may be written to investigate those differences more fully.

Inclusion of Women and Minorities:

This study will be open to all individuals regardless of gender, ethnicity, or race provided that the aforementioned inclusion and exclusion criteria are met. The table below includes accrual estimates for the duration of the study.

Accrual Targets					
Ethnic Category	Sex/Gender				
	Females		Males		Total
Hispanic or Latino	8	+	8	=	16
Not Hispanic or Latino	26	+	18	=	44
Ethnic Category: Total of all subjects	34 (A1)	+	26 (B1)	=	60 (C1)
Racial Category					
American Indian or Alaskan Native	0	+	0	=	0
Asian	2	+	2	=	4
Black or African American	4	+	4	=	8
Native Hawaiian or other Pacific Islander	0	+	0	=	0
White	28	+	20	=	48
Racial Category: Total of all subjects	34 (A2)	+	26 (B2)	=	60 (C2)

(A1 = A2)

(B1 = B2)

(C1 = C2)

Accrual Rate: 4 pts/month **Total Expected Accrual:** 54 Min 60 Max

6.2 Justification for Exclusions

Pregnant women are excluded from this study because AZD2171 is a VEGF inhibitor with known abortifacient effects. Because there is an unknown but potential risk for adverse events in nursing infants secondary to treatment of the mother with AZD2171, breastfeeding should be discontinued if the mother is treated with AZD2171. Participants with unstable or serious medical conditions such as uncontrolled diabetes, uncontrolled hypertension, symptomatic congestive heart failure, unstable angina pectoris, myocardial infarction within the past 6 months, uncontrolled cardiac arrhythmia; or psychiatric illness/social situations that would limit compliance with study requirements are excluded due to the possibility that the underlying condition may obscure the attribution of effect and adverse events and may limit study compliance. HIV-positive patients on combination antiretroviral therapy are ineligible because of the potential for pharmacokinetic interactions with AZD2171.

Appropriate studies will be undertaken in patients receiving combination antiretroviral therapy when indicated.

6.3 Participation of Children

This study includes patients under 16 years of age. Given the recent results of the Phase I study in children [28], exploration of the activity in this patient population is warranted. Enrollment of children will be limited to those with a minimum BSA of 0.63 m² and those who are able to swallow tablets for safe dosing with AZD2171. Appropriate safeguards for toxicity monitoring, particularly for toxicity related to hypertension or effects on bone growth, are included in the protocol design.

6.4 Evaluation of Benefits and Risks/Discomforts

There may or may not be any clinical benefit to a patient from participation in this trial. Their participation will benefit future cancer patients. Potential risks include the possible occurrence of any of a range of side effects that are listed in the consent document. The procedure for protecting against or minimizing risks will be to medically evaluate patients as described in protocol Section 6.6. Although no compensation is available, any injury will be fully evaluated and treated in keeping with the benefits or care to which participants are entitled under applicable regulations.

6.5 Consent and Assent Process and Documentation

An associate or principal investigator on the trial will inform patients or patient's parents or guardian if he/she is a child of the purpose, alternatives, drug administration plan, research objectives and follow-up of this trial. The patient will be provided an IRB-approved consent for review and signature and his/her questions will be answered. After a decision is made to enroll into the study, a signature will be obtained from the patient. The original signed consent goes to Medical Records; a copy will be placed in the research record. Patients will not be consented by telephone.

All patients must have a signed informed consent form and an on-study (confirmation of eligibility) form filled out and signed by a participating investigator before entering on study.

The investigators are requesting a waiver from the IRB to allow only one parent to sign the informed consent to enter a child on the protocol. Because many patients must travel to the NIH from long distances at substantial expense, requiring both parents to be present for the consent process could be a financial hardship for many families. Where deemed appropriate by the clinician and the child's parents or guardian, the child will also be included in all discussions about the trial and verbal or written assent will be obtained depending on the age of the child. The parent or guardian will sign the designated line on the informed consent attesting to the fact that the child has given assent.

Adults unable to give consent are excluded from enrolling in the protocol. However, re-consent may be necessary, and there is a possibility, though unlikely, that subjects could become decisionally impaired. For this reason, and because there is a prospect of direct benefit from research participation, all subjects \geq age 18 at the NCI only will be offered the opportunity to fill in their wishes for research and care, and assign a substitute decision maker on the "NIH Advance Directive for Health Care and Medical Research Participation" form so that another person can make decisions about their medical care in the event that they become incapacitated or cognitively impaired during the course of the study. Note: The PI or AI will contact the NIH Ability to Consent Assessment Team for evaluation. For those subjects that become incapacitated and do not have pre-determined substitute decision maker, the procedures described in MEC Policy 87-4 for appointing a surrogate decision maker for adult subjects who are (a) decisionally impaired, and (b) who do not have a legal guardian or durable power of attorney, will be followed.

6.6 Procedure for Protecting Against or Minimizing Any Potential Risks

All care will be taken to minimize side effects, but they can be unpredictable in nature and severity. This study may involve risks to patients, which are currently unforeseeable. All patients will be monitored for side effects from taking study medication. This research represents a greater than minimal risk to participants, but presents the prospect of direct benefit to individual subjects.

Pediatric patients: This trial is open to children under 16 years of age. The primary risk to patients participating in this research study is as stated above. Therefore, this protocol involves greater than minimal risk to children, but presents the potential for direct benefit to individual subjects. As noted above, safeguards will be implemented for early detection and treatment of possible toxicities.

6.6.1 *Patient Advocate*

The patients' rights representative is available to patients receiving treatment on this protocol at the NIH Clinical Center at [contact] in [name], on the Bethesda NIH campus. Patients enrolled at other sites will be given information regarding their local patient advocate. Patients will be informed that they can contact the study PI or RN at any time with questions about their medical care, and that the patients' rights representative is also available to answer non-medical questions about the study.

7 Adverse Events: List And Reporting Requirements

7.1 Comprehensive Adverse Events and Potential Risks List (CAEPR)

CAEPR for Cediranib (AZD2171, NSC 732208)

The Comprehensive Adverse Events and Potential Risks list (CAEPR) provides a single list of reported and/or potential adverse events (AE) associated with an agent using a uniform presentation of events by body system. In addition to the comprehensive list, a subset, the Specific Protocol Exceptions to Expedited Reporting (SPEER), appears in a separate column and is identified with bold and italicized text. This subset of AEs (SPEER) is a list of events that are protocol specific exceptions to expedited reporting to NCI (except as noted below). Refer to the 'CTEP, NCI Guidelines: Adverse Event Reporting Requirements' http://ctep.cancer.gov/protocolDevelopment/electronic_applications/docs/aeguidelines.pdf for further clarification. Frequency is provided based on 1608 patients. Below is the CAEPR for Cediranib (AZD2171).

NOTE: Report AEs on the SPEER **ONLY IF** they exceed the grade noted in parentheses next to the AE in the SPEER. If this CAEPR is part of a combination protocol using multiple investigational agents and has an AE listed on different SPEERs, use the lower of the grades to determine if expedited reporting is required.

Adverse Events with Possible Relationship to Cediranib (AZD2171) (CTCAE 5.0 Term) [n= 1608]			Specific Protocol Exceptions to Expedited Reporting (SPEER)
Likely (>20%)	Less Likely (<=20%)	Rare but Serious (<3%)	
BLOOD AND LYMPHATIC SYSTEM DISORDERS			
		Hemolytic uremic syndrome	
		Thrombotic thrombocytopenic purpura	
CARDIAC DISORDERS			
		Heart failure	
		Left ventricular systolic dysfunction	
ENDOCRINE DISORDERS			
	Hyperthyroidism		
	Hypothyroidism		Hypothyroidism (Gr 2)
GASTROINTESTINAL DISORDERS			
	Abdominal pain		Abdominal pain (Gr 3)
	Anal mucositis		Anal mucositis (Gr 2)
	Constipation		Constipation (Gr 3)
Diarrhea			Diarrhea (Gr 3)
	Dry mouth		Dry mouth (Gr 2)
	Dysphagia		Dysphagia (Gr 2)
		Gastrointestinal fistula ²	
		Gastrointestinal perforation ³	
	Mucositis oral		Mucositis oral (Gr 3)
Nausea			Nausea (Gr 3)
		Pancreatitis	
	Rectal mucositis		Rectal mucositis (Gr 2)
	Small intestinal mucositis		Small intestinal mucositis (Gr 2)
	Vomiting		Vomiting (Gr 3)
GENERAL DISORDERS AND ADMINISTRATION SITE CONDITIONS			
Fatigue			Fatigue (Gr 3)
HEPATOBILIARY DISORDERS			
		Hepatic failure	
INFECTIONS AND INFESTATIONS			
	Infection ⁴		
INJURY, POISONING AND PROCEDURAL COMPLICATIONS			
		Wound complication	
INVESTIGATIONS			

Adverse Events with Possible Relationship to Cediranib (AZD2171) (CTCAE 5.0 Term) [n= 1608]			Specific Protocol Exceptions to Expedited Reporting (SPEER)
Likely (>20%)	Less Likely (<=20%)	Rare but Serious (<3%)	
	Alanine aminotransferase increased		Alanine aminotransferase increased (Gr 3)
	Alkaline phosphatase increased		
	Aspartate aminotransferase increased		Aspartate aminotransferase increased (Gr 3)
	Lymphocyte count decreased		
	Neutrophil count decreased		
	Platelet count decreased		
	Thyroid stimulating hormone increased		Thyroid stimulating hormone increased (Gr 2)
	Weight loss		Weight loss (Gr 2)
METABOLISM AND NUTRITION DISORDERS			
Anorexia			Anorexia (Gr 3)
	Dehydration		Dehydration (Gr 3)
	Hypophosphatemia		Hypophosphatemia (Gr 3)
MUSCULOSKELETAL AND CONNECTIVE TISSUE DISORDERS			
	Generalized muscle weakness		
NERVOUS SYSTEM DISORDERS			
	Dizziness		Dizziness (Gr 2)
	Headache		Headache (Gr 3)
	Lethargy		
		Leukoencephalopathy	
		Reversible posterior leukoencephalopathy syndrome	
RENAL AND URINARY DISORDERS			
		Nephrotic syndrome	
	Proteinuria		Proteinuria (Gr 2)
RESPIRATORY, THORACIC AND MEDIASTINAL DISORDERS			
	Cough		Cough (Gr 2)
	Dyspnea		Dyspnea (Gr 3)
	Laryngeal mucositis		Laryngeal mucositis (Gr 2)
	Pharyngeal mucositis		Pharyngeal mucositis (Gr 2)
	Tracheal mucositis		Tracheal mucositis (Gr 2)
Voice alteration			Voice alteration (Gr 2)
SKIN AND SUBCUTANEOUS TISSUE DISORDERS			

Adverse Events with Possible Relationship to Cediranib (AZD2171) (CTCAE 5.0 Term) [n= 1608]			Specific Protocol Exceptions to Expedited Reporting (SPEER)
Likely (>20%)	Less Likely (<=20%)	Rare but Serious (<3%)	
	Palmar-plantar erythrodysesthesia syndrome		Palmar-plantar erythrodysesthesia syndrome (Gr 2)
VASCULAR DISORDERS			
		Arterial thromboembolism	
Hypertension			Hypertension (Gr 3)
	Thromboembolic event		Thromboembolic event (Gr 4)
	Vascular disorders - Other (hemorrhage) ⁵		

¹This table will be updated as the toxicity profile of the agent is revised. Updates will be distributed to all Principal Investigators at the time of revision. The current version can be obtained by contacting [contact]. Your name, the name of the investigator, the protocol and the agent should be included in the e-mail.

²Gastrointestinal fistula includes Anal fistula, Colonic fistula, Duodenal fistula, Esophageal fistula, Enterovesical fistula, Gastric fistula, Gastrointestinal fistula, Ileal fistula, Jejunal fistula, Oral cavity fistula, Pancreatic fistula, Rectal fistula, and Salivary gland fistula under the GASTROINTESTINAL DISORDERS SOC.

³Gastrointestinal perforation includes Colonic perforation, Duodenal perforation, Esophageal perforation, Gastric perforation, Ileal perforation, Jejunal perforation, Rectal perforation, and Small intestinal perforation under the GASTROINTESTINAL DISORDERS SOC.

⁴Infections includes all 75 sites of infection under the INFECTIONS AND INFESTATIONS SOC.

⁵Hemorrhage is a known consequence of VEGF/VEGFR signaling inhibition. The majority of hemorrhage events reported were mild; however, serious events, defined as symptomatic bleeding in a critical area or organ system (e.g., eye, gastrointestinal tract, genitourinary [GU] tract, respiratory tract, and nervous system) have been reported.

Adverse events reported on cediranib (AZD2171) trials, but for which there is insufficient evidence to suggest that there was a reasonable possibility that cediranib (AZD2171) caused the adverse event:

BLOOD AND LYMPHATIC SYSTEM DISORDERS - Anemia; Blood and lymphatic system disorders - Other (polycythemia); Bone marrow hypocellular; Febrile neutropenia

CARDIAC DISORDERS - Atrial fibrillation; Atrial flutter; Cardiac arrest; Cardiac disorders - Other (premature ventricular complexes); Cardiac disorders - Other (valvular heart disease); Chest pain - cardiac; Mobitz (type) II atrioventricular block; Myocardial infarction; Palpitations; Pericardial effusion; Pericarditis; Restrictive cardiomyopathy; Sinus bradycardia; Sinus tachycardia; Supraventricular tachycardia

EAR AND LABYRINTH DISORDERS - Ear and labyrinth disorders - Other (ears feel full/plugged); Ear and labyrinth disorders - Other (viral labyrinthitis); Tinnitus; Vertigo

EYE DISORDERS - Blurred vision; Eye disorders - Other (blindness); Eye disorders - Other (visual disturbance); Papilledema; Photophobia; Retinal vascular disorder

GASTROINTESTINAL DISORDERS - Abdominal distension; Anal pain; Ascites; Bloating; Colitis; Colonic obstruction; Duodenal ulcer; Dyspepsia; Enterocolitis; Esophageal necrosis; Esophageal ulcer; Esophagitis; Flatulence; Gastric necrosis; Gastric ulcer; Gastroesophageal reflux disease; Gastrointestinal disorders - Other (diverticulitis); Gastrointestinal disorders - Other (hydrops); Gastrointestinal disorders - Other (tongue sensitivity); Ileus; Oral pain; Periodontal disease; Peritoneal necrosis; Rectal pain; Small intestinal obstruction

GENERAL DISORDERS AND ADMINISTRATION SITE CONDITIONS - Chills; Edema face; Edema limbs; Fever; Gait disturbance; Hypothermia; Malaise; Non-cardiac chest pain; Pain

HEPATOBILIARY DISORDERS - Cholecystitis; Gallbladder obstruction; Hepatic pain; Hepatobiliary disorders - Other (bile duct obstruction); Hepatobiliary disorders - Other (jaundice cholestatic)

IMMUNE SYSTEM DISORDERS - Allergic reaction; Anaphylaxis; Immune system disorders - Other (systemic inflammatory response syndrome)

INJURY, POISONING AND PROCEDURAL COMPLICATIONS - Bruising; Dermatitis radiation; Fracture; Injury, poisoning and procedural complications - Other (tracheostomy malfunction); Intestinal stoma leak; Venous injury; Wound dehiscence

INVESTIGATIONS - Activated partial thromboplastin time prolonged; Blood bilirubin increased; Blood lactate dehydrogenase increased; CPK increased; Cardiac troponin I increased; Cardiac troponin T increased; Cholesterol high; Creatinine increased; Ejection fraction decreased; Electrocardiogram QT corrected interval prolonged; GGT increased; Hemoglobin increased; INR increased; Investigations - Other (elevated ammonia level); Investigations - Other (increased blood erythropoietin); Lipase increased; White blood cell decreased

METABOLISM AND NUTRITION DISORDERS - Acidosis; Hypercalcemia; Hyperglycemia; Hyperkalemia; Hypertriglyceridemia; Hypoalbuminemia; Hypocalcemia; Hypoglycemia; Hypokalemia; Hypomagnesemia; Hyponatremia; Metabolism and nutrition disorders - Other (failure to thrive)

MUSCULOSKELETAL AND CONNECTIVE TISSUE DISORDERS - Arthralgia; Avascular necrosis; Back pain; Bone pain; Chest wall pain; Muscle cramp; Muscle weakness lower limb; Muscle weakness upper limb; Myalgia; Myositis; Neck pain; Pain in extremity; Rotator cuff injury

NEOPLASMS BENIGN, MALIGNANT AND UNSPECIFIED (INCL CYSTS AND POLYPS) - Tumor pain

NERVOUS SYSTEM DISORDERS - Ataxia; Central nervous system necrosis; Cognitive disturbance; Depressed level of consciousness; Dysarthria; Dysgeusia; Dysphasia; Encephalopathy; Hydrocephalus; Ischemia cerebrovascular; Memory impairment; Muscle weakness left-sided; Nervous system disorders - Other (coma); Nervous system disorders - Other (right hemiparesis); Olfactory nerve disorder; Peripheral motor neuropathy; Peripheral sensory

neuropathy; Seizure; Somnolence; Spinal cord compression; Stroke; Syncope; Transient ischemic attacks; Tremor

PSYCHIATRIC DISORDERS - Confusion; Delirium; Depression; Hallucinations; Insomnia; Suicide attempt

RENAL AND URINARY DISORDERS - Acute kidney injury; Chronic kidney disease; Cystitis noninfective; Hematuria; Urinary retention; Urinary tract obstruction

REPRODUCTIVE SYSTEM AND BREAST DISORDERS - Irregular menstruation; Menorrhagia; Vaginal fistula

RESPIRATORY, THORACIC AND MEDIASTINAL DISORDERS - Aspiration; Hypoxia; Pharyngolaryngeal pain; Pleural effusion; Pneumonitis; Pneumothorax; Pulmonary edema; Pulmonary fistula; Pulmonary hypertension; Sinus pain

SKIN AND SUBCUTANEOUS TISSUE DISORDERS - Alopecia; Dry skin; Hyperhidrosis; Nail loss; Pruritus; Purpura; Rash acneiform; Rash maculo-papular; Skin and subcutaneous tissue disorders - Other (petechiae); Skin and subcutaneous tissue disorders - Other (plantar warts); Skin ulceration; Urticaria

VASCULAR DISORDERS - Capillary leak syndrome; Flushing; Hypotension; Vasculitis

Note: Cediranib (AZD2171) in combination with other agents could cause an exacerbation of any adverse event currently known to be caused by the other agent, or the combination may result in events never previously associated with either agent.

